### **4.3 Informing the subject's healthcare provider**

In countries where applicable, and only if the subject agrees in writing in the informed consent form and is treated by a healthcare provider, e.g., general practitioner, the subject's healthcare provider should be informed about the subject's participation in the trial at the time of enrollment. The healthcare provider should be informed about the trial code, the principal investigator's name, and a contact (telephone) number at the trial site.

Any communication with the healthcare provider must be documented in the subject's medical records or the investigator's site file.

## **5 INVESTIGATORS AND TRIAL ADMINISTRATIVE STRUCTURE**

### **5.1 Investigators and trial site personnel**

#### **5.1.1 Investigators**

There must be an investigator at each trial site.

If the trial is conducted by a team of individuals at the trial site, the investigator leading and responsible for the team is called the principal investigator.

All persons assigned responsibility as principal investigator must sign a declaration of their responsibilities and their agreement to this protocol before any trial-related procedure is performed.

Curriculum vitae and/or other relevant documents confirming the current qualification of the investigators must be provided to the sponsor. This should include any previous training in the principles of GCP, experience obtained from work with clinical trials, and experience with subject care.

Documentation of all involved investigators must be maintained according to GCP and applicable regulatory requirements.

In different countries, there may be country-specific terminology used for the investigator role.

Country-specific coordinating investigators will be defined who are responsible for the coordination of principal investigators at multiple trial sites in 1 country.

An international coordinating investigator will be defined who is responsible for the coordination of principal investigators at multiple trial sites in multiple countries.

Documentation of all responsibilities assigned to the country-specific coordinating investigators/international coordinating investigator must be maintained according to GCP and applicable regulatory requirements.

#### **5.1.2 Trial site personnel assigned trial-related duties**

The principal investigator may define appropriately qualified personnel at a trial site to perform significant trial-related procedures and/or to make trial-related decisions under his/her supervision. In this case, the principal investigator must maintain a signed list of the persons to whom they delegate significant trial-related duties/responsibilities; the delegated trial-related duties/responsibilities must be specified in the list.

When personnel or responsibility changes are made, the principal investigator must ensure that the relevant documentation is updated before any trial-related activities are performed.

Documentation of all involved trial site personnel performing significant trial-related procedures and/or making trial-related decisions must be maintained according to GCP and applicable regulatory requirements.

## **5.2 Contract research organizations**

Contract research organizations (CROs; commercial, academic or other, e.g., central laboratory facilities, trial supply management provider, electronic patient reported outcome provider) may be contracted by the sponsor to perform trial-related duties and functions. The extent of the delegation must be documented. All involved CROs will be required to have implemented quality control and quality assurance processes, and to support the sponsor's quality control and quality assurance measures.

Documentation of all involved CROs must be maintained according to GCP and applicable regulatory requirements. Documentation of any delegation of responsibilities to CROs must be maintained in the trial master file.

## **5.3 The sponsor and sponsor's personnel**

The trial sponsor listed on the title page accepts the responsibilities of the sponsor according to GCP and applicable regulatory requirements.

The sponsor must designate appropriately qualified personnel to advise on trial-related topics. The trial site will be provided with contact details for these personnel before any trial-related procedure is performed.

A list of key sponsor personnel involved in the preparation of this protocol and the conduct of the trial, including their full names, titles, roles, and responsibilities, must be maintained.

A list of key personnel contracted by the sponsor and involved in the conduct of the trial including their full names, addresses, and responsibilities, must be maintained.

## **5.4 Data monitoring committee**

An external, independent data monitoring committee (DMC) will periodically review safety information from the trial and monitor trial conduct and overall progress.

The DMC will have the ability to make recommendations to the sponsor that might impact the future conduct of the trial. Procedures for and management of the DMC will follow the sponsor's standard operating procedures (SOPs) and will be documented in the DMC Charter. The DMC for this trial is anticipated to convene approximately every 6 months, depending on subject accrual in the trial.

---

## 6 INTRODUCTION AND TRIAL BACKGROUND

### 6.1 Introduction

Complex regional pain syndrome is a chronic, severe and frequently disabling condition that can develop after a minor injury, such as a fracture or sprain, usually in a distal extremity (hand, wrist, ankle, and foot). CRPS is characterized by disproportionate pain, relative to the inciting event, and signs and symptoms related to sensory, vasomotor and sudomotor abnormalities, trophic changes (abnormal skin, hair, and nails), and impaired motor function in the affected limb (Harden et al. 2010a). There are currently no approved pharmacological treatments for CRPS in the US, and patients are underserved due to a poor understanding of the pathophysiological processes and lack of evidence for effective treatments (Harden et al. 2013; Goebel 2013; Bruehl 2015).

Randomized placebo-controlled trials of bisphosphonates in patients with CRPS indicate that these agents are efficacious for treatment of pain and other symptoms associated with this syndrome (Brunner et al. 2009; Cossins et al. 2013; O'Connell et al. 2013; Varenna et al. 2013; Wertli et al. 2014). Since bisphosphonates act to suppress osteoclastic bone resorption, it is likely that bone pathology plays a role in the evolution and maintenance of CRPS Type I (CRPS-I; Gatti et al. 2016), although other mechanisms may be involved (Varenna et al. 2013). Evidence of osteopenia and increased uptake of radiolabeled bisphosphonate tracer (observed during bone scintigraphy) in the affected limb(s) of patients with CRPS provides support for this hypothesis. Therefore, the present open-label trial with a total dose of neridronic acid 400 mg is designed to obtain safety information to support the potential broader use of neridronic acid to address a major unmet medical need in patients with CRPS.

### 6.2 Background to the IMP

Neridronic acid is an alkyl-aminobisphosphonate with a chemical structure and potency similar to that of pamidronate (Gatti et al. 2013). Neridronic acid has been studied in subjects with Paget's disease of bone, osteogenesis imperfecta, hypercalcemia, and osteoporosis and has been marketed in Italy under the tradename NERIXIA® for treatment of osteogenesis imperfecta since 2002 and for Paget's disease since 2006. In 2014, NERIXIA received market authorization for treatment of CRPS in Italy.

### 6.3 Relevant non-clinical and clinical data

For a detailed summary of relevant non-clinical and clinical experience, see the current edition of the neridronic acid investigator's brochure.

More than 500 subjects have received parenteral neridronic acid in Phase II and Phase III trials intended for registration of intravenous or intramuscular formulations for the treatment of osteogenesis imperfecta, Paget's disease, osteoporosis, and CRPS-I. Doses administered in these trials ranged from 12.5 mg to 400 mg, with the 400 mg dose administered as either a single intravenous infusion of approximately 5 hours, or divided into four 2-hour infusions of 100 mg administered over 10 days. Based on results of these trials, neridronic acid appears safe and well tolerated up to a dose of 400 mg as a single or divided infusion. Drug-related adverse events following intravenous and intramuscular administration of neridronic acid consisted predominantly

of fever and flu-like symptoms (e.g., arthralgia, myalgia) following the first administration, as well as pain, bruising, and tenderness at the injection site for intramuscular injections. Mean decreases in calcium and phosphate were noted in serum chemistry assessments, although individual subject out-of-range values and symptomatic hypocalcemia were rare. Based on these findings, the adverse event profile of neridronic acid is considered to be similar to that of other aminobisphosphonates. The safety of neridronic acid is supported by spontaneous adverse event reporting, pharmacovigilance, and information from published trials.

In a multi-site, placebo-controlled trial of intravenous neridronic acid in 82 subjects with CRPS-I receiving 400 mg of neridronic acid, administered as four 2-hour infusions of 100 mg on Day 1, Day 4, Day 7, and Day 10, a statistically significantly greater percentage of subjects experienced at least 50% decrease in pain intensity at 40 days after the first infusion compared with placebo (73.2% for neridronic acid versus 32.5% for placebo [treatment difference: 40.7%; 95% confidence interval: 18.7%, 59.5%];  $p = 0.0003$ ). Secondary endpoints, including change from baseline in pain intensity, pain evoked by passive motion, edema, active range of motion, hyperalgesia, and allodynia, also showed significant improvements (Varenna et al. 2013). There were no serious or severe adverse events in the neridronic acid treatment group. The most frequent adverse events were arthralgia, fever, and headache, consistent with the acute phase reaction. These results suggest intravenous neridronic acid 400 mg is effective and safe for treatment of CRPS-I.

## 6.4 Trial rationale

The aim of this trial is to investigate the safety of intravenous neridronic acid in patients with CRPS. The trial is intended as an integral part of the overall safety assessment of neridronic acid, to support submission to regulatory agencies for product registration.

## 7 TRIAL OBJECTIVES AND ENDPOINTS

The trial objectives and endpoints are given in Section 1.2.

## 8 TRIAL DESIGN

### 8.1 Discussion of the trial design

This is a multi-site, open-label, single-arm, Phase III trial. A single-arm trial, without a placebo or other comparator, maximizes the number of subjects exposed to neridronic acid and is intended to provide adequate safety data to support product registration. Although efficacy assessments are included for exploratory purposes, results of these evaluations must be interpreted with caution in the absence of a comparator arm.

A subset of subjects will undergo iliac crest bone biopsy to assess bone histology and histomorphometry indices following treatment with neridronic acid 400 mg. The effect of neridronic acid on bone quality and mineralization was evaluated in biopsies from 14 patients with Paget's disease receiving neridronic acid 250 mg (50 mg/day for 5 days; McCloskey et al. 1987; Atkins et al. 1987). Normal bone mineralization and bone formation were observed in biopsies from regions of non-pagetetic bone (iliac crest), and improved indices of bone turnover were observed in

regions of pagetic bone. It is planned to obtain approximately 15 evaluable bone biopsy specimens from approximately 20 subjects. It is anticipated that bone biopsy specimen evaluation will confirm normal bone mineralization in the iliac crest at approximately 6 months following treatment with neridronic acid 400 mg. A 6 month time point was selected for the biopsy in order to match the slow kinetics of bone matrix and mineral apposition in humans, with approximately 6 months required to complete a single remodeling cycle (Riggs and Parfitt 2005).

It is anticipated that a subset of 30 subjects will undergo bone densitometry and MRI to assess the effect of neridronic acid on BMD and bone marrow lesions in CRPS-affected limbs, relative to the contralateral, unaffected limb. The same subject will be allowed to participate in both bone biopsy and bone densitometry and MRI sub studies if they are willing. This exploratory investigation is anticipated to corroborate published descriptions of decreased BMD and other bone abnormalities in the affected limbs of subjects with CRPS (Gatti et al. 2016) and may provide a foundation for future investigation of the effect neridronic acid on bone pathology in CRPS.

### **Rationale for the trial population**

The trial population will include subjects with both CRPS-I and CRPS Type II (CRPS-II). Subjects with CRPS-II are poorly represented in clinical trials. However, the distinctions between these two subtypes are not always clear (Oaklander and Horowitz 2015; Bruehl 2015). Inclusion of subjects with CRPS-II is not anticipated to affect the safety objectives of this trial.

#### **8.1.1 Rationale for the investigational medicinal product and the selected dose**

A placebo-controlled trial in 82 subjects with CRPS-I indicated that 400 mg of neridronic acid, administered as four 2-hour infusions of 100 mg in 10 days, is safe, well-tolerated and effective for treatment of pain and other symptoms of CRPS (Varenna et al. 2013).

A pilot trial of neridronic acid involving cumulative intravenous doses of 200 mg, 300 mg, and 400 mg neridronic acid in patients with CRPS-I suggested that the 400 mg cumulative dose was optimally effective. As the 4 x 100 mg dose regimen has been approved for treatment of CRPS-I in Italy, the same dose regimen was selected for investigation in this trial.

In Italy, the recommended infusion time for neridronic acid 100 mg to treat Paget's disease of bone, osteogenesis imperfecta, and CRPS-I is 2 hours. To limit the maximum concentrations ( $C_{max}$ ) in this trial to levels similar to those obtained in the KF7013-01 trial, in which neridronic acid 62.5 mg was infused in 2 hours, the infusion time has been extended to 4 hours.

Alternative dosage forms or routes of administration for neridronic acid are limited to an intramuscular dosage form (25 mg per ampule, available in Italy), which would be impractical for administering a 400 mg total dose. An oral dosage form is not available and would have practical limitations due to the very low bioavailability of bisphosphonates (typically reported in the range of 1%).

#### **8.1.2 Rationale for the number and the frequency of visits/assessments**

The number of visits and visit frequency are the same as those in the previous KF7013-01 trial and are considered sufficient to assure subject safety and meet study objectives.

---

## 8.2 Benefit/risk analysis

Potential benefits to subjects participating in this trial may include a reduction in pain and other symptoms of CRPS, as well as benefits of medical supervision from being in a clinical trial.

Risks to subjects participating in this trial are primarily related to the known side effects of neridronic acid and bisphosphonates as a class, particularly those associated with intravenous administration. Although doses of up to 400 mg of neridronic acid have been administered safely in subjects with Paget's disease or CRPS-I, most of the clinical experience for neridronic acid has been at doses of 200 mg or below. In addition to drug-specific risks, there are also the risks of the procedures used in the trial.

In order to minimize the risk for the subject, it is obligatory that the investigator becomes familiar with all sections of the current neridronic acid investigator's brochure prior to the initiation of the trial and follows the warnings and directions thereof.

The trial population described in this protocol will consist of subjects with a diagnosis of CRPS and who are medically stable and in stable follow-up therapy for CRPS for at least 1 month.

Subjects will continue to receive stable therapy for CRPS. Additional pain medication may be prescribed in the event of severe pain flare, with notification of the sponsor. Changes in analgesic medications and other treatments for CRPS may be permitted during the follow-up period. This will help to ensure that subjects in the trial will not suffer from untreated pain. Subjects may withdraw from the trial at any time, without giving a reason and without prejudice. However, subjects who withdraw will be asked to continue follow-up visits if at all possible for the scientific integrity of the trial as well as for their own safety.

### **Potential risks and risk management of neridronic acid**

#### *Acute phase reaction*

The most common side effects associated with parenteral administration of aminobisphosphonates are flu-like symptoms, commonly referred to as "acute phase reaction" (Reid et al. 2010; Silverman et al. 2011). Symptoms include fever, myalgia, fatigue, headache, diarrhea, arthralgia, muscle pain, and bone pain. These are self-limiting and usually resolve after 24 hours to 48 hours. Symptoms of the acute phase reaction typically occur following the first administration and are absent or decreased following subsequent administrations. For symptomatic management of the acute phase reaction, oral acetaminophen (paracetamol), is recommended, starting from approximately 1 hour prior to the first infusion and then approximately every 6 hours for the 72-hour period after the first infusion. Commercially available products and dosages can be used as available in the country where the trial is performed. However, the total dose of acetaminophen, including any other medications that contain acetaminophen, must not exceed 4 g/day, due to acetaminophen's known risks for hepatic toxicity. Non-steroidal anti-inflammatory drugs should not be used to alleviate the symptoms of the acute phase reaction due to their potential to cause acute changes in renal function, which may confound renal safety assessments.

#### *Ocular effects*

Eye disorders have been reported with neridronic acid and appear to be associated with the acute phase reaction. These events include anterior uveitis, episcleritis, conjunctivitis and ocular pain. As severe ocular inflammation may increase the potential risk of long-term vision loss, treatment with

neridronic acid will be discontinued at first signs of ocular inflammation, followed by an ophthalmologic exam.

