### 9.3.2 Subject discontinuation from the IMP

Discontinuation of IMP applies only to the treatment period. Subjects who are discontinued from IMP should not be discontinued from the trial except for the reasons indicated in [Table 1](#). Subjects who are discontinued from IMP should be encouraged to remain in the trial for their own safety and for the integrity of the trial.

Subjects must be evaluated prior to each infusion of IMP. The investigator must permanently or temporarily discontinue treatment with IMP for any reasons listed in [Table 2](#). The investigator may decide to temporarily discontinue a subject from receiving IMP for other reasons if further assessments may be helpful to assure safety of the subject. The investigator may also choose to permanently discontinue a subject from treatment if they believe that continued exposure of the subject to neridronic acid may pose an undue risk to the subject, e.g., due to particular adverse events or due to deterioration in the subject's health for reasons related or unrelated to the treatment.

In situations where treatment is temporarily discontinued, the treatment period may be extended to a maximum of 21 days (i.e., Visit 5 should occur no later than 21 days after Visit 2). Visit 6 will be scheduled to occur 4 days ( $\pm 2$  days) after Visit 5, but all subsequent visits should occur as originally scheduled relative to Visit 2 (e.g., Visit 7 will be 42 days [6 weeks] after Visit 2). No more than 4 infusions may be administered during the treatment period, and a minimum of 48 hours between any 2 infusions is required.

Table 2: Reasons for permanent and temporary discontinuation of subjects from IMP

Reason	Discontinuation from IMP	
	Permanent	Temporary
Symptomatic hypocalcemia.	X	
Serum calcium <7.8 mg/dL (<1.95 mmol/L). The subject may resume treatment following investigator assessment and a repeat serum calcium value above this limit (albumin-corrected serum calcium should be considered if serum albumin is below 3.5 g/dL).		X
Clinical signs of dehydration (e.g., dizziness, palpitations, confusion).		X
Evidence suggestive of a possible change in renal function:		

 
A persistent <math>\geq 25\%</math> decrease from baseline (last value observed prior to treatment) in the eGFR, based on repeated central laboratory results from blood samples obtained at least 1 week apart a.
 
	X	

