
 
A <math>\geq 25\%</math> decrease from baseline in the eGFR. If a repeated measurement of eGFR is within 75% or more of the baseline value, the subject may resume treatment a.
 
		X

 
A persistent urinary ACR >300 mg/g based on quantitative urinary albumin and creatinine data from the central laboratory, with urine samples obtained at least 1 week apart.
 
	X	

 
A urinary ACR >300 mg/g based on the results of the semi-quantitative dipstick or quantitative data from the central laboratory. The subject may resume treatment if quantitative urinary albumin and creatinine data from the central laboratory indicate a urinary ACR value <150 mg/g.
 
		X

 
A persistent eGFR <50 mL/min/1.73 m^2 and urinary ACR >150 mg/g based on repeated quantitative data from the central laboratory, with blood and urine samples obtained at least 1 week apart.
 
	X	
An average QTcF interval of >500 ms based on triplicate ECGs, or average QTcF interval of >480 ms with a concurrent increase in average QTcF interval >60 ms relative to the average of triplicate ECGs obtained at Visit 1.	X	
Pregnancy.	X	
Development of hypersensitivity to the IMP.	X	
Signs or symptoms of ocular inflammation: b		

 
Resolution of signs and symptoms within 5 days.
 
		X

 
Persistent or recurrent signs and symptoms.
 
	X	

Reason	Discontinuation from IMP	
	Permanent	Temporary
At any point during the treatment period if further assessment may be helpful to assure safety of the subject.		X
Any other adverse event causing a significant deterioration in subject's health.		X
Major protocol deviations (e.g., serious non-compliance with protocol procedures, unsafe use of prohibited medication, abuse of illicit drugs, or other reckless behavior during the trial that may jeopardize the subject's safety or safety of other subjects or site staff).	X	

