a) Baseline values of eGFR are obtained from central laboratory results after Visit 2 (based on the blood sample taken at Visit 2 prior to the first administration of IMP). Evaluation of change from baseline in eGFR must occur prior to Visit 4 and Visit 5, based on assessment of central laboratory results from blood samples taken prior to Visit 3 and Visit 4, respectively.

b) Subjects should be assessed for ocular inflammation by the investigator prior to each infusion (signs and symptoms include eye redness and irritation, blurred vision, eye pain, and sensitivity to light). Subjects with signs or symptoms of ocular inflammation should be temporarily suspended from treatment. Subjects with resolution of signs and symptoms within 5 days may resume treatment. Subjects with persistent or recurrent signs and symptoms of ocular inflammation must be discontinued from IMP and undergo an ophthalmologic examination.

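### Section 8.2 ties an eye examination to the first ocular signs, whereas footnote b of Table 2 mandates it for persistent or recurrent signs and allows re-dosing without it if signs resolve within 5 days

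*Protocol*

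**What the plan says.** Two parts of the current protocol deal with ocular inflammation during treatment.

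- **Section 8.2, ocular effects.** After giving possible lasting loss of vision as the reason for caution, it says that "neridronic acid will be discontinued at first signs of ocular inflammation, followed by an ophthalmologic exam". It sets no condition of persistence or recurrence, mentions no resumption, and does not refer to Section 9.3.2.
- **Section 9.3.2, Table 2.** There are two ocular rows. "Resolution of signs and symptoms within 5 days" is marked in the temporary column. "Persistent or recurrent signs and symptoms" is marked in the permanent column.
- **Section 9.3.2, footnote b to Table 2.** On the first response: "Subjects with signs or symptoms of ocular inflammation should be temporarily suspended from treatment". On restarting: "Subjects with resolution of signs and symptoms within 5 days may resume treatment". On the examination: "Subjects with persistent or recurrent signs and symptoms of ocular inflammation must be discontinued from IMP and undergo an ophthalmologic examination". The footnote names no other trigger for an ophthalmologic examination.

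The text above Table 2 governs how the table is used: "The investigator must permanently or temporarily discontinue treatment with IMP for any reasons listed in" Table 2.

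**The concern.** Section 8.2 presents stopping and a specialist examination as the way the risk to vision is managed, and the favorable benefit/risk conclusion rests on that section. If the rule applied at the infusion visits asks for the examination in fewer situations, the stated justification does not describe what will happen to some subjects.

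The event is foreseeable. Section 8.2 lists anterior uveitis among the eye disorders reported with neridronic acid, and Section 18.1 includes uveitis among the concepts to consider when judging seriousness. Ocular signs are to be checked before each infusion, so sites will meet the rule repeatedly. At stake is whether a subject with a short ocular episode must see an ophthalmologist, and whether that can be left out before re-dosing.

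**Working it through.** The documents give no figure to reproduce, so the check compares the two rules for each course an ocular episode can take.

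| Course of signs | Section 8.2 | Table 2 and footnote b | Do they agree on the examination? |
|---|---|---|---|
| Persist beyond 5 days | Stop; examination | Permanent stop; examination mandated | Yes |
| Resolve within 5 days, later recur | Stop; examination after first signs | Suspension, possible restart, then permanent stop and examination on recurrence | Mandated under both; footnote b attaches it to the recurrence |
| Resolve within 5 days, no recurrence | Stop; examination after first signs | Suspension, possible restart; no examination mandated | **No** |

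Only the third row is a contradiction that no reading removes. Section 8.2 attaches the examination to first signs without condition. Footnote b describes the same subject, permits a restart, and mandates the examination for a different group.

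**Largest number of infusions affected.** Four infusions are planned. If signs are found at the check before infusion k, then 4 − (k − 1) infusions remain:

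- k = 2: 4 − 1 = 3
- k = 3: 4 − 2 = 2
- k = 4: 4 − 3 = 1

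The maximum of 3 can be reached. If signs are found at Visit 3 (Day 4) and resolve after 5 days, that is Day 4 + 5 = Day 9. With the minimum of 48 hours between infusions, the three remaining infusions could fall on Days 9, 11 and 13. The limit for Visit 5 is 21 days after Visit 2, that is Day 1 + 21 = Day 22.

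**Action on treatment.** Section 8.2 says neither temporary nor permanent. The text of Section 9.3.2 and the title of Table 2 use discontinuation for both. Under the temporary reading, Section 8.2 and footnote b agree on the first response; under the permanent reading they do not. The wording does not settle which is meant. By contrast, the renal paragraphs of Section 8.2 send the reader to Section 9.3.2 for the stopping criteria.

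**Link to the analysis.** The secondary safety endpoint counts permanent stops of treatment for adverse events. The CRF separates interruption from withdrawal of drug (protocol Section 12.3.1). SAP Section 8.2.2 defines subjects discontinued from treatment as those stopped permanently, and SAP Section 20.1.2.1 takes the reasons from the eCRF. The count therefore follows what sites do and record. It moves only if a site takes Section 8.2 to mean a permanent stop. Membership of the Treatment Completers Set, which requires all 4 full infusions, carries the same condition.

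**The case against.** The best defense is that the operative rule is easy to find. Section 10.2 requires the Section 9.3.2 criteria to be evaluated before each infusion, and the checklists for all four infusion visits refer to that section. Section 8.2 is a benefit/risk narrative and may simply be a compressed summary. The rationale for Amendment 02 says that discontinuation becomes permanent when eye symptoms return, which implies that a first episode was not meant to be permanent.

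Much of this stands, and it rules out several stronger readings that a reader might infer:

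- **That the two sections plainly contradict each other on stopping treatment.** They do not, because the protocol uses the same word for both kinds of stop. This part is an ambiguity.
- **That every subject with any ocular sign is affected.** Where signs persist or recur, both texts lead to an examination.
- **That subjects are re-dosed with no eye check.** Footnote b calls for investigator assessment before each infusion, and an investigator may order more. What is absent is a mandated ophthalmologic examination.
- **That the secondary endpoint is altered.** This depends on a site reading Section 8.2 as permanent despite the columns of Table 2.
- **That the data monitoring committee works to a different rule.** Section 5.4 leaves its procedures to a charter, and nothing shows that it applies an ocular rule from Section 8.2.

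The defense does not reach the examination trigger. Locating the operative rule in Section 9.3.2 tells a site what to follow. It does not make the Section 8.2 statement true for an episode that clears within 5 days. Nothing says that Section 8.2 is a summary or that footnote b prevails.

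**Conclusion.** The point holds for the examination trigger. For a subject whose ocular signs resolve within 5 days and do not recur, Section 8.2 calls for an ophthalmologic examination and footnote b lets treatment resume with none mandated. Up to 3 further infusions could follow. The number of such subjects cannot be estimated, because the documents give no rate of ocular events.

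That footnote b limits the mandate to persistent or recurrent signs is inferred from its naming no other trigger; it does not use the word *only*. Whether stopping at first signs is temporary or permanent is unclear in Section 8.2, with a conditional effect on the count of permanent discontinuations and on the Treatment Completers Set. The texts should be reconciled. This is a clarification of limited reach, and it implies no view on which clinical rule is right.

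**What to change.** Reconcile Section 8.2, Table 2 and footnote b so that all three state one rule on two matters:

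1. When the ophthalmologic examination is required, including for an episode that resolves within 5 days.
2. Whether stopping at first signs is temporary or permanent and, if temporary, on what condition treatment may resume.

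A reference from the ocular paragraph of Section 8.2 to Section 9.3.2 would help keep them aligned, as the renal paragraphs already do. The sponsor's clinical team decides which rule applies.

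The cost is protocol wording in one amendment or clarification letter. The endpoint definitions and the SAP's counting rules need no change.
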